2.1.1 General definitions

Study treatment or drug

In future sections through this document, ‘study treatment’ or ‘study drug’ will be used to refer to investigational therapy assigned to a patient. Specifically, for the double-blind treatment phase, study treatment refers to LCZ696 or ramipril as assigned to a patient at randomization.

Screening epoch or screening period

Screening epoch or screening period is defined as the period starting from date of signed of informed consent until date of randomization or decision on randomization.

Randomized treatment phase

The randomized treatment phase begins at the time of randomization and ends with the last study drug intake or the death of the patient, whichever comes earlier. During the randomized treatment phase, patients will return for scheduled clinic visits. For all related safety analyses randomized treatment starts with the first intake of randomized, double-blind study drug. Temporary interruption of the study drug will not be counted as randomized treatment phase discontinuation.

Post-treatment follow-up phase

The post-treatment follow-up phase (usually after premature permanent study drug discontinuation) begins after last study drug intake + 1 day and ends on the date last seen (or vital status confirmed by indirect contact).

Double-blind period or double-blind treatment epoch

The double-blind period, also called the double-blind treatment epoch, is the combination of the randomized treatment phase and the post-treatment follow-up phase.

Baseline and study day

For analysis purpose, baseline value for all variables is defined to be the last results obtained at or prior to randomization date (or prior to 1st study drug intake for safety assessments). Most of variables will have their baseline at visit 101, unless otherwise specified. [REDACTED]

Study day of any assessment refers to the number of days to the assessment relative to randomization (day 1), or relative to the 1st study drug intake for safety assessments.

Unscheduled visit

Only for the analysis of safety laboratory evaluation will unscheduled measurements be taken into account. For efficacy evaluations, measurements from unscheduled visits will generally not be used, unless specifically specified.

On-treatment data for an efficacy endpoint

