The estimand targeted in the original study protocol is defined in Table 2-3. In comparison, in a hypothetical world without COVID-19, the new intercurrent event due to COVID-19 is the onset of COVID-19 pandemic impact on study (see Table 2-4), which can be derived by a fixed global COVID-19 impact start date (01-Mar-

2020) or subject-specific impact start date based on information from the COVID CRF pages. A hypothetical strategy (see below methods i and ii) will be used for this new intercurrent event.

The analyses targeting this estimand will be performed with the following censoring methods:

- i. Endpoint data will be censored on 29-Feb-2020 if the patient has not experienced the endpoint by this time

This analysis will be performed using the primary analysis model as specified in [Section 2.5.2](#).

- ii. Endpoint data will be censored at the time of subject-specific COVID-19 impact start date, derived as the earliest date of the following for each patient based on the COVID-19 eCRF: (a1) study treatment discontinuation due to COVID-19; (a2) start of treatment interruption for > 3 months due to COVID-19; (b) first missed visit due to COVID-19; (c) first endpoint event impacted by COVID-19; (d) symptom onset of the first occurrence of a condition for which the patient felt the need to go to an outpatient clinic, urgent care, emergency department, or hospital but chose not to due to COVID-19.

This analysis will be performed using inverse probability of censoring weighted (IPCW) Cox proportional hazards model (Robins and Finkelstein 2000) as described in Section 2.6.5. IPCW is used to account for potential informative censoring using the subject-specific censoring method.

Table 2-3 Estimand in the original protocol :

Intercurrent event	Strategy
Permanent treatment discontinuation	Treatment policy strategy
Non-CV death	Hypothetical strategy

Primary scientific question of interest / Estimand:
 
What would be the relative risk reduction (HR) for Entresto vs Ramipril (regardless of treatment discontinuation) in patients with LV systolic dysfunction and/or pulmonary congestion following an AMI, in the composite primary endpoint, as measured by the time to first composite of CV death, HFH and outpatient HF, in the absence of death from non-CV related causes?
	

Table 2-4 Estimand in a world without the COVID-19 pandemic:

Intercurrent event	Strategy
Permanent treatment discontinuation	Treatment policy strategy

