Estimating IPC weights

In order to predict these patient specific time-varying probabilities, the time scale is split into small intervals based on the visit schedules. In each interval the conditional probability of being switched given patient has not switched at any earlier interval is modelled using a logistic regression model with the following covariates–

- **Time independent (baseline) covariates:**

Age (in years), baseline LVEF, baseline eGFR (ml/min/1.73m²), history of prior MI (yes/no), history of diabetes (yes/ no), Atrial Fibrillation associated with qualifying MI (yes/no), baseline Killip class, use of PCI for qualifying MI (yes/ no), use of ACEI/ARB in last 24 hours prior to randomization (yes/ no), use of IV treatment for qualifying MI (yes/ no)

- **Time dependent covariates:**

Systolic BP (mmHg), Heart rate (bpm), eGFR (ml/min/1.73m²), *use of PCI or CABG (yes/ no), *use of ICD/CRT (yes / no)

*(*procedures related to any post-randomization MI event)*

Predicted probability of switching at a specific time for a patient will be obtained by multiplying individual conditional probabilities of switching in intervals prior to that time point. To minimize impact of extreme weights (e.g. patients not switched though having very high estimated probability to switch), the stabilized version of weights will be used which is defined as the ratio of predicted probabilities of not being switched by time t –

- from the logistic regression with only baseline covariates
- from the logistic regression with both baseline and post-baseline covariates

It is conceivable that the above logistic regression procedure of estimating weights may not converge due to reasons including (but not limited to) sparseness of switchers in the subpopulations implied by the selected covariates resulting into an infinite likelihood due to complete or quasi-complete separation or numerical difficulties in evaluating an overly complex likelihood function. Should such problems arise, the logistic regression model used to determine the IPC weights will be simplified by pooling pre-specified time intervals (thereby extending the time windows in which time-dependent covariates are assessed). If that still does not solve convergence problems, the model will be simplified by removing covariates.

All patients randomized to LCZ696 will be assigned a weight of 1 for all time intervals.

Estimation of treatment effect

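### One patient-level COVID-19 censoring trigger is back-dated to the start of a drug interruption that must later pass 3 months, so censoring depends on the future; the effect is small

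*SAP*

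**What the plan says.** Method ii under item 2(2) of the sensitivity and supplementary analyses in SAP 2.5.4 censors the primary endpoint at a patient-specific date, "derived as the earliest date of the following for each patient based on the COVID-19 eCRF". There are five triggers:

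- (a1) study treatment discontinued because of COVID-19;
- "a2) start of treatment interruption for > 3 months due to COVID-19";
- (b) the earliest visit that the patient missed because of the pandemic;
- (c) the earliest endpoint event that the pandemic affected;
- (d) onset of symptoms for which the patient stayed away from care because of COVID-19.

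The remedy offered for dependent censoring is a weighted Cox model taken from SAP 2.6.5: "IPCW is used to account for potential informative censoring using the subject-specific censoring method". In SAP 2.6.5, "the conditional probability of being switched given patient has not switched at any earlier interval is modelled using a logistic regression model". A switch there means a ramipril patient starting open-label Entresto, and "All patients randomized to LCZ696 will be assigned a weight of 1 for all time intervals".

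SAP 2.1 sets the final cut-off at 31-Dec-2020. SAP 2.1.1 says that the randomized treatment phase "ends with the last study drug intake or the death of the patient, whichever comes earlier", and that a temporary interruption does not end it. Neither document says how to treat an interruption cut short by death, by an endpoint event or by the cut-off.

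**The concern.** Whether a patient is censored at time t should be decidable from what is known at t. Trigger (a2) breaks this rule: the date is the start of the interruption, but the condition is settled more than 3 months later, and survival and restart of drug in between help to settle it. Follow-up kept after the start is therefore selected partly on outcome.

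Method ii is the only patient-level analysis of the estimand in SAP Table 2-4 (a world without the pandemic); method i uses one calendar date for everyone. SAP 2.5.4 allows analyses of that estimand to be read as addressing the question in the study protocol. The situation is also real: the rationale for Protocol Amendment 4 reports interruptions caused by pandemic supply problems, without a count.

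**Working it through.** **1. The rule applied to cases.** Let S be the start of a COVID-19 interruption, with no other trigger coming first.

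| After S | Under (a2) |
|---|---|
| CV death at S + 2 months | Trigger not met; time and death kept |
| Event-free, still off drug past S + 3 months | Censored at S; all later follow-up lost |
| HF event at S + 1, drug restarted at S + 2 | Event kept |
| HF event at S + 1, still off drug past S + 3 | Censored at S; event lost |
| S after about 30-Sep-2020 | Cannot exceed 3 months by 31-Dec-2020; trigger not met |

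Rows 3 and 4 have the same history up to the event and are treated differently because of what follows.

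**2. Why weighting does not help.** The weights at t are built from baseline covariates and covariates observed up to t. They can balance patients who are censored for reasons visible by then. They cannot undo censoring at S that was decided by survival and restart after S. As written, the SAP 2.6.5 model also describes a different event, in one arm only.

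**3. Check on the inputs.** The documents give no figure for (a2), so only the planning inputs can be reproduced.

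- Events for 80% power at HR 0.81, two-sided 0.05: 4 × (1.960 + 0.842)² / (ln 0.81)² = 31.40 / 0.0444 = 707.1, rounded up to 708, as stated.
- Monthly hazard for months 12 to 18 (SAP Table 3-4 and its footnote: 11.0% and 13.0%): ln(0.89/0.87)/6 = 0.0038. Extended to 32 months: 1 − 0.87 × exp(−14 × 0.00379) = 17.5%, as stated.
- Months 3 to 6 (7.2% and 8.6%): ln(0.928/0.914)/3 = 0.0051.

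**4. Events within 3 months of S.** The risk is 1 − exp(−3 × 0.00379) = 1.13% at the later hazard, and 1 − exp(−3 × 0.00507) = 1.5% for patients in months 3 to 6. The share of patients who start an interruption is assumed.

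- 5% of 5,650 = 283 patients: 3.2 to 4.3 events.
- 10% = 565 patients: 6.4 to 8.6 events.

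Only part of these are CV deaths. The gap at 18 months between the primary composite (13.0%) and HF hospitalization or outpatient HF (10.3%, SAP Table 3-6 footnote) suggests a share of about 2.7/13.0 = 21%; 40% is taken as an assumed upper value. At the later hazard that is 0.7 to 1.3 deaths at 5% and 1.3 to 2.6 at 10%.

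**5. Effect on the hazard ratio.** A simulation of 2 million patients, scaled to 5,650, used the Table 3-4 hazards, the SAP accrual pattern and HR 0.81, with (a2) as the censoring rule and no weights. Assumptions from outside the documents: a 10-month COVID-19 period at study months 37 to 47; 5% to 30% of an arm interrupting; CV deaths 30% or 40% of first events; interruptions averaging 4 months or never ending.

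- The true event rate in the 3 months after S was 0.048 to 0.054 per year. In the follow-up that (a2) retains it was 0.059 to 0.29 per year, about 1.2 to 5.6 times as high.
- Equal interruption by arm: HR shift at most 0.0002, because the same selection acts in both arms.
- Three-fold imbalance: shift 0.0004 to 0.005. With 15% of ramipril and 5% of LCZ696 patients interrupting, the HR went from 0.8111 to 0.8069; reversed, from 0.8076 to 0.8123.
- The largest shift is ln(0.8123/0.8076) = 0.0058 on the log scale, against a standard error of √(4/708) = 0.075, so under one-tenth of it.
- Censoring at every S, or at S + 3 months if still interrupted, gave the uncensored HR to within 0.001 in every scenario.

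**The case against.** The strongest reply is that (a2) is one of five triggers and the earliest applies. Drug is dispensed to last until the next visit (Protocol 5.5.4), with extra supply for delays (Protocol 5.1.1), and visits are 4-monthly after month 4. A supply-driven interruption will often follow a missed visit, so (b) has already censored the patient. A CV death during the interruption might be flagged under (c). A patient who dies without restarting might be recorded as a COVID-19 discontinuation under (a1), since the Protocol glossary defines discontinuation as stopping permanently, and under SAP 2.1.1 the treatment phase would have ended at the last intake.

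This stands as a limit. A reader might infer that every CV death in the window is retained and that only event-free time is removed. The documents support neither: other triggers may remove the death, and some non-fatal events are removed as well. How (a1) and (c) are recorded depends on a COVID-19 eCRF that is not in the documents. The reply does not remove the defect, because SAP 2.3.1 also anticipates off-site visits and changed dispensing, so an interruption need not come with a missed visit.

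It can also be said that dating impact at its onset suits the estimand and that the 3-month threshold sensibly ignores brief gaps. Both are fair aims, but a start date combined with a later condition cannot serve them together without looking ahead.

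**Conclusion.** The concern holds for trigger (a2) on its natural reading, that the interruption must actually last more than 3 months, and for patients whom no other trigger censors first. It is minor. A few events at most are exposed under assumed interruption rates of 5% to 10%.

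A reader might infer that any difference between arms in interruptions carries over in full to the hazard ratio. The simulation does not support that: even a three-fold imbalance moved it by no more than 0.005, and double-blind, double-dummy supply makes such an imbalance unlikely. Nor should the exposed events be set only against those accrued after 1-Mar-2020, since method ii also uses all earlier events; against 708, 3.2 to 8.6 events is 0.5% to 1.2%. These figures use pre-pandemic hazards, and Amendment 4 reports fewer HF events during the pandemic, so they may be too high.

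Method i, the primary test and the alpha allocation are unaffected.

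**What to change.** Replace (a2) with a date known when it occurs, applied alike to fatal and non-fatal events. Either option works:

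- **Censor 3 months after the start if the COVID-19 interruption is still continuing.** Cost: up to 3 months of off-drug follow-up after the onset of impact stays in, which fits the Table 2-4 estimand less closely.
- **Censor at the start of every COVID-19 interruption, whatever its length.** Cost: brief gaps count as COVID-19 impact and some follow-up is lost.

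Under either rule, death, an endpoint event or the cut-off within the 3 months needs no special handling. Choose one before database lock and, if wished, report the other as a check. The work is one line of SAP text and one derivation. The same edit should say that the weights for method ii model COVID-19 censoring in both arms, since the text of SAP 2.6.5 does not.

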Non-CV death	Hypothetical strategy
Onset of COVID-19 pandemic impact on study	Hypothetical strategy

Primary scientific question of interest / Estimand:
 
What would be the relative risk reduction (HR) for Entresto vs Ramipril (regardless of treatment discontinuation) in patients with LV systolic dysfunction and/or pulmonary congestion following an AMI, in the composite primary endpoint, as measured by the time to first composite of CV death, HFH and outpatient HF, in the absence of COVID-19 pandemic and death from non-CV related causes?
	

Since the study was designed without a COVID-19 pandemic in mind, both the analysis targeting the estimand “in a world without COVID-19 pandemic” and the primary analysis based on all data up to the end-of-study analysis cut-off may be interpreted as addressing the estimand in the original study protocol, acknowledging that the treatment effect estimate based on the latter might be affected by the pandemic.

(3) Bayesian analysis with robust prior

Let us denote by $y_{pre} = \log(\widehat{HR}_{pre})$ the observed log(hazard ratio) based on data obtained **before** the global outbreak of COVID-19, and by $y_{post} = \log(\widehat{HR}_{post})$ the observed log(hazard ratio) based on data obtained **after** the outbreak. The true underlying log(hazard ratio) is denoted by θ . We use the normal approximation for the log(hazard ratio), and thus, when denoting the number of events by n_{pre} , n_{post} , we obtain for the likelihood

$$y_{pre} | \theta \sim N\left(\theta, \frac{4}{n_{pre}}\right)$$

$$y_{post} | \theta \sim N\left(\theta, \frac{4}{n_{post}}\right)$$

Our goal is to leverage the information obtained after the outbreak to inform the hazard ratio from the data obtained before the outbreak. However, since the impact of COVID-19 on the endpoint is unclear, we aim doing so in a robust way. Therefore, we build a prior for θ that fulfills the following two requirements:

- In case of similarity of y_{pre} and y_{post} , the information obtained after the outbreak is, to a substantial extent, taken into account
- In case of a conflict between y_{pre} and y_{post} , the information obtained after the outbreak is down-weighted in a dynamic way

These requirements can be addressed using a robust mixture prior (see e.g. Schmidli et al, 2014) consisting of two components:

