Component 1: Informative prior distribution $p_{inf}(\theta) = N(y_{post}, \frac{4}{n_{post}})$, which is the posterior distribution of θ given y_{post} , when starting with an improper prior for θ

Component 2: Vague prior distribution $p_{vague}(\theta) = N(y_{post}, 2^2)$, which is a vague (unit-information) prior distribution for θ

The robust mixture prior is obtained by mixing these distributions with weights w and $1 - w$, respectively:

$$p(\theta) = w * p_{inf}(\theta) + (1 - w) * p_{vague}(\theta)$$

Finally, we obtain the posterior distribution $p(\theta|y_{pre})$ through standard Bayesian updating. As a fact of mixture calculus, the posterior is a mixture of the component-wise posteriors, but with updated weights:

$$p(\theta|y_{pre}) = \tilde{w} \times p_{inf}(\theta|y_{pre}) + (1 - \tilde{w}) \times p_{vague}(\theta|y_{pre})$$

where $p_x(\theta|y_{pre})$ is the posterior distribution of θ given data y_{pre} and prior $x \in \{inf, vague\}$.

The weights are updated according to the following rule:

$$\tilde{w} = \frac{w * m}{w * m + (1 - w) * m'}$$

$$m = \int p(y_{pre}|\theta)p_{inf}(\theta)d\theta$$

$$m' = \int p(y_{pre}|\theta)p_{vague}(\theta)d\theta$$

Finally, the weights chosen for the analysis are $w = 1 - w = 0.5$, i.e. we a priori assume there is an equal chance of similarity and conflict between y_{pre} and y_{post} . This choice is common practice in applications (Dominguez et al, 2017). The point estimate and 95% probability interval will be obtained from this posterior distribution as the median and 2.5th and 97.5th percentile, respectively. Furthermore, the posterior probability that the hazard ratio is favoring LCZ696 (i.e., $HR < 1$), will be provided. SAS code for this analysis can be found in Appendix 5.4.

- (4) Analysis of all CEC-confirmed primary endpoint data accrued up to the end-of-study analysis cut-off, using a Cox model with a “during-COVID” indicator and its interaction with treatment as time-varying covariates.

Consider the following model:

$$h(t) = h_0(t)\exp(\beta_1 \times trt + \beta_2 \times \mathbb{I}\{C(t)\} + \beta_3 \times \mathbb{I}\{C(t)\} \times trt),$$

where $\mathbb{I}\{C(t)\}$ is an indicator of “during-COVID” at patient-time t . $\mathbb{I}\{C(t)\}$ is equal to 1 if the patient-time t falls in the COVID-19 impacted period (on or after 1-Mar-2020), and is equal to 0 otherwise.

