This analysis model will allow the assessment of the treatment effect in non-COVID impacted periods (before and after the COVID-impacted period, estimated by β_1). It will also allow to quantify the change in event rate during the COVID-impacted period (β_2) and the change of the treatment effect during the COVID-impacted period (β_3), however the number of events and hence precision may be low. In addition to including treatment, “during-COVID” indicator, treatment by “during-COVID” indicator interaction as covariates, this model will also adjust for region and PCI use at baseline, and be stratified by type of MI (STEMI/NSTEMI).

- (5) Weibull regression model stratified by type of MI (STEMI/NSTEMI), with treatment, PCI use at baseline and region included as factors in the model, including all CEC-confirmed primary endpoint events that occurred prior to 01-Mar-2020. Parametric model may be more powerful than the semiparametric primary model.
- (6) Analysis with adjustment of country instead of region in the primary analysis model as specified in [Section 2.5.2](#), both using all CEC-confirmed primary endpoint data accrued up to the end-of-study analysis cut-off and event data with onset date prior to 01-Mar-2020. This may recover some of the lost power by accounting for the heterogeneity of the COVID-19 impact and also the standard of care among countries within regions)

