There are two points to be considered in the sample size re-estimation: the estimated lower event rates and a potentially higher hazard reduction in the primary endpoint. As shown in [Table 3-4](#) and [Table 3-5](#), the estimated event rates using blinded data are lower than the originally assumed event rates, for both the primary endpoint (see [Table 3-4](#)) and the double composite endpoint (see [Table 3-5](#)). An RRR of 19% is assumed for the primary endpoint in place of the original RRR of 18%. This change is based on the newly available efficacy data from the PIONEER-HF (CLCZ696BUS01) study in hospitalized patients with stabilized acute decompensated heart failure, which showed a 46% relative risk reduction (HR 0.54, 95% CI 0.37, 0.79) in patients treated with sacubitril/valsartan for 8 weeks compared to enalapril for an exploratory composite of serious clinical endpoint of death, rehospitalization for heart failure, implantation of a left ventricular assist device, and inclusion on the list of patients eligible for heart transplantation (Velazquez, et al. 2019). The observed risk reduction on the composite endpoint from the PIONEER-HF study was primarily driven by rehospitalization. Given a similar underlined pathophysiological mechanism between HFrEF and post-AMI with left ventricular dysfunction, and also acute setting for both PIONEER-HF and PARADISE-MI studies, this new data indicated that the effect size may have previously been underestimated.

Following the blinded sample size re-estimation, a sample size of 5,650 patients, randomized to LCZ696:ramipril using a 1:1 allocation ratio, has been chosen with the aim to obtain at least 708 first primary endpoint events and at least 592 first CV death or HF hospitalization events in this event-driven study. Seven hundred eight primary endpoint events will provide 80% power assuming a true Relative Risk Reduction (RRR) of 19% (i.e. a hazard ratio of 0.81) for LCZ696 vs ramipril with statistical testing at the overall 2.5% 1-sided type I error rate (with strong control of the FWER). Five hundred ninety two first CV death or HF hospitalization events will provide 77.5% nominal power assuming a true RRR of 20% (for the ITT analysis) for this double composite endpoint for the same type I error rate.

Additional assumptions are described below.

- 0.5% per year lost to follow-up rate (same as the original protocol assumption)

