- Recruitment duration of 37 months, and approximately 4 months follow-up for the last randomized patient are assumed (i.e., approximately 41 months for endpoint accrual). Constant recruitment rates are assumed in each of the following time period based on the observed PARADISE-MI study data and projection: (1) 0 to 10 months, with a total of 463 patients randomized by month 10; (2) 10 to 24 months, with approximately a total of 2400 patients randomized by month 24; (3) 24 to 37 months, with 250 patients randomized each month.
- One interim analysis is planned to allow for stopping for efficacy, using a Haybittle-Peto boundary, thus 2.49% 1-sided alpha will be available for the final analysis, see Section 2.14.
- Cumulative event rates for the primary composite endpoint at 3, 6, 12, and 18 months were derived based on Kaplan-Meier estimates using blinded data from all randomized patients in the PARADISE-MI study at the time of sample size re-estimation. Constant

piecewise hazard rates were then derived accordingly for the following time periods: 0 to 3 months, 3 to 6 months, 6 to 12 months, and 12 to 41 months. The hazard rate for the time period of 12 to 41 months was derived through extrapolation of the 18 months cumulative event rate assuming a constant hazard rate during this time period. See [Table 3-4](#) for the cumulative event rates (pooled) based on the originally assumed event rates from [Table 3-1](#), as well as the estimated event rates from the blinded sample size re-estimation.

Table 3-4 Cumulative event rates (pooled) for the primary endpoint (first CV death, HF hospitalization or outpatient HF event)

Time from randomization	Cumulative event rate (original assumption) ²	Cumulative event rate (estimated using blinded data)
3 months	10.3%	7.2%
6 months	12.8%	8.6%
12 months	15.4%	11.0%
32 months ¹	20.1%	17.5%

¹ 32 months event rates were derived through extrapolation of the 18 months cumulative event rates, assuming constant monthly hazard rates from 12 to 32 months. The 18 months cumulative event rate was estimated to be 13.0% for the primary endpoint (first CV death, HF hospitalization or outpatient HF event).

² Cumulative event rates (pooled) were derived according to the original assumption of the control group rates in [Table 3-1](#).

Table 3-5 Cumulative event rates (pooled) for the double composite endpoint (first CV death or HF hospitalization event)

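### The during-COVID treatment interaction in SAP 2.5.4 item 2(4) cannot separate a pandemic effect from a treatment effect that changes with time since the MI

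*SAP*

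**What the plan says.** SAP 2.5.4 lists these analyses for the case where the trial continues past the second interim analysis.

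- **Item 2(4)** fits h(t) = h0(t) exp(beta_1 × trt + beta_2 × I{C(t)} + beta_3 × I{C(t)} × trt), stratified by type of MI and adjusted for region and PCI. The indicator is 1 if patient-time t "falls in the COVID-19 impacted period (on or after 1-Mar-2020), and is equal to 0 otherwise". Beta_3 is described as "the change of the treatment effect during the COVID-impacted period", with one caveat, that precision may be low. Beta_1 is described as the treatment effect in non-impacted periods both before and after the COVID period.
- **Item 2(3)** is a Bayesian analysis with a robust mixture prior. If the pre- and post-outbreak log hazard ratios disagree, "the information obtained after the outbreak is down-weighted in a dynamic way".
- **SAP 2.5.2** assumes that the hazard ratio does not depend on time within each stratum.
- **SAP 3.2** splits follow-up when it uses the blinded event rates: "piecewise hazard rates were then derived accordingly for the following time periods: 0 to 3 months, 3 to 6 months, 6 to 12". The last interval starts at month 12 and runs to month 41.

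**The concern.** The baseline hazard h0(t) runs on patient-time, so it absorbs the steep fall in event rate after the MI. It does not absorb a treatment effect that differs between the early and later phases. The COVID indicator follows the calendar, and by March 2020 the cohort is mostly in later follow-up, so calendar period and time since MI are strongly associated. (Randomization is 12 hours to 7 days after presentation, so time since randomization is close to time since MI.)

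These analyses are meant to show whether the pandemic altered the result. An effect that wanes after the MI would look like attenuation during COVID, and one that builds would look like enhancement. The stated caveat about precision does not cover this.

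Separately, the indicator stays at 1 from 1-Mar-2020 to the 31-Dec-2020 cut-off. There is no later non-impacted period, so beta_1 rests on pre-March-2020 person-time alone.

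**Working it through.** **1. Reproduce the plan.** For HR 0.81, one-sided 2.49% and 80% power, Schoenfeld's formula 4(z_alpha + z_beta)²/(ln HR)² gives 708 events, as stated in SAP 3.2.

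**2. Hazards.** The blinded cumulative rates (SAP Table 3-4 and its footnote) are 7.2, 8.6, 11.0 and 13.0% at 3, 6, 12 and 18 months. Taking differences of -ln(1 - rate) and dividing by interval length gives 0.0249, 0.0051, 0.0044 and 0.0038 per month. The first is 6.6 times the last.

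**3. Accrual.** SAP 3.2 gives 463 patients by month 10, 2,400 by month 24, then 250 per month to month 37, with 0.5% loss per year. With the hazards above this gives 710 primary events at month 41 (plan: 708) and 17.5% at 32 months (as stated).

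**4. Calendar anchor (an assumption).** Protocol Amendment 3, dated 01-May-2019, reports over 3,500 randomized. Month = 24 + (3,500 - 2,400)/250 = 28.4, so 1-Mar-2020, ten months later, is month 38.4 and 31-Dec-2020 about month 48.4. Since 3,500 is a lower bound, 3,700 would give 24 + 1,300/250 + 10 = 39.2.

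**5. Share of primary events in months 0-3 after randomization.**

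| Recruitment assumed | Before 1-Mar-2020 | From 1-Mar-2020 |
|---|---|---|
| As projected, ends month 37 | 60-61% | 1-4% |
| Slower, ends at 1-Mar-2020 | 59-61% | 11% |
| Slower, ends 1-3 months after | 59-61% | 16-23% |

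The upper end moves by a point or two with how the delay is spread. The range is needed because the documents give no last-randomization date, SAP 2.3.1 provides for patients randomized on or after 1-Mar-2020, and the projection gives 650-672 events before that date against 0.80 × 708 = 566 expected (540 in the code in SAP 5.4).

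**6. Effect on beta_3 with no COVID effect.** To a close approximation, beta_3 = (pre share - post share) × ln(HR later / HR early). Assume HR 0.75 in months 0-3 and 0.92 later, so the log ratio is ln(0.92/0.75) = 0.204.
- Post share 4%: (0.61 - 0.04) × 0.204 = 0.116, exp = 1.12.
- Post share 20%: (0.60 - 0.20) × 0.204 = 0.082, exp = 1.09.

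Fitting the model to expected counts (without stratum and covariates) gives the same values. With a standard error of about 0.16, ln 1.12 = 0.113 is 0.7 SE. Other assumed patterns on projected recruitment:

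| HR months 0-3 / later | exp(beta_3) |
|---|---|
| 0.81 / 0.81 | 1.00 |
| 0.70 / 1.00 | 1.21 |
| 0.90 / 0.72 | 0.87 |
| 0.95 / 0.65 | 0.79 |

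The largest shift is about 1.4 SE.

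**7. Which time terms are enough.** With a single step at month 3, one treatment × (months 0-3) term returns exp(beta_3) to 1.00. With gradual waning (assumed HR 0.75/0.80/0.85/0.95 over the four SAP intervals), exp(beta_3) is 1.14 unadjusted, 1.05 with that single term, and 1.00 with treatment terms over all four intervals. The SE rises from about 0.16 to 0.19 with the single term and to about 0.20 with all four intervals.

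**8. Item 2(3).** With 540 and 184 events, the updated weight is m/(m + m'). Here m and m' are normal densities of the log-HR difference with variances 4/540 + 4/184 = 0.0291 and 4/540 + 4 = 4.007. The weight on the informative component is 0.92 when the two HRs agree, 0.91 at a ratio of 1.11 and 0.86 at 1.21.

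**The case against.** The strongest reply is that the SAP assumes a constant hazard ratio and the documents contain no evidence against it. Under that assumption beta_3 is unbiased. This stands: the bias is conditional, and the HR patterns above are assumptions. But a model fitted to detect a changing HR should not depend on constancy to explain the change. The protocol also gives reasons why the effect could vary by phase: stepwise titration over the first weeks, and open-label ACE inhibitor or ARB after study drug is stopped, in a treatment-policy analysis.

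Three stronger readings are tempting, and the documents do not support them.

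- A reader might infer that the SAP attributes beta_3, or prior-data conflict, to COVID. Its wording for beta_3 describes a calendar window, and item 2(3) calls the pandemic's impact unclear and down-weights on any conflict.
- A reader might infer that almost no post-period events are early. That holds only on projected recruitment, which overshoots the expected pre-March-2020 count by at least 650 - 566 = 84 events.
- A reader might infer that the Bayesian analysis would discard sound late data. The weight moves only from 0.92 to 0.86-0.91.

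It is also fair to say that these are two of several supplementary analyses, and that the analysis censored at 29-Feb-2020, item 2(2)i, involves no pre/post contrast.

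**Conclusion.** The gap is real but modest. As specified, a non-zero beta_3 cannot be assigned to the pandemic, because the two periods sample different phases after the MI (about 60% against about 1-23% of events in months 0-3) and nothing in the model allows the treatment effect to vary by phase. For the assumed 0.75-then-0.92 pattern the spurious exp(beta_3) is about 1.09-1.12, under one SE. If the HR is constant it is 1.00. The shares rest on the SAP's blinded hazards, its projected recruitment and the calendar anchor.

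The primary analysis and its alpha are not touched. The error in the description of beta_1 needs no assumption: it follows from how the indicator is defined and from the cut-off date.

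**What to change.** 1. Beside the planned item 2(4) model, report a version that adds treatment-by-time-since-randomization terms over the SAP's own intervals (0-3, 3-6, 6-12 and >12 months). A single cut at 3 months is not enough if the effect changes gradually.
2. State that beta_3, or pre/post conflict in item 2(3), will not be attributed to COVID unless the interaction persists in that version.
3. In the description of beta_1, delete *and after*.

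A separate Bayesian run restricted to late follow-up is not needed, because the weight barely moves.

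The cost is one extra model fit and some SAP wording, with no new data. The downside is precision: the SE of beta_3 rises from about 0.16 to about 0.20 on projected recruitment, for an estimate the SAP already expects to be imprecise.
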